Specific Aim 1: Assess the safety and feasibility of a new holding protocol for stable infants undergoing therapeutic hypothermia in the NICU. We hypothesize that there will not be a significant change in temperature variation, and there will be no increase in adverse events during holding.

Specific Aim 2: Assess mothers' and nurses' qualitative experience related to the holding during hypothermia intervention using a questionnaire with a combination of closed and open-ended questions. We hypothesize that mothers and nurses will respond positively to the opportunity to hold during hypothermia.

Adverse Effects: Given the vulnerability of infants in the NICU, potential adverse effects of the holding intervention and the monitoring strategy for these adverse effects are outlined here.

1. Holding during hypothermia could result in unintentional rewarming of the infant due to the proximity of the normothermic mother. In order to prevent rewarming, a thermal barrier will be placed between the mother and infant and the infant's esophageal temperature will be monitored every two minutes during holding and the intervention stopped early if the infant rewarms more than 1°C. Retrospective review of 16 medical records of infants treated with hypothermia at Maine Medical Center with gestational ages ranging from 34 -40+ weeks document a usual range of temperatures during cooling from 33-34°C (goal is 33.5°C)¹⁰. The research team has made the determination that the intervention will be stopped early if the infant rewarms more than 1°C based on this data.

2. Holding during hypothermia could result in dislodging of central lines. Only experienced NICU nurses will move the infant from the isolette into the mother's arms with assistance from a member of the research team. Critically ill infants that are intubated are considered too great a risk for accidental extubation and are therefore excluded.

C. Materials and Methods

Study Design: This is a single center safety study of the feasibility of a novel holding protocol for infants undergoing therapeutic hypothermia.

Study Population: As this is a pilot study to investigate concept and feasibility, a convenience sample of ten infants and their mothers in the MMC NICU being treated with TH will be recruited for the study according to the following criteria:

Inclusion criteria:

- Infant with gestational age ≥ 35 weeks treated with therapeutic hypothermia
- Infant **without** seizures in the first 24 hours on EEG

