- Infants who are clinically stable on bubble CPAP, nasal cannula or who have no respiratory support. This criterion MUST be confirmed by the Attending Neonatologist.
- Infants with all types of vascular access are eligible.
 - Use appropriate caution and attention to peripheral arterial lines and central lines (PICC, UAC, UVC, tunneled central catheters)
- Informed consent for research study signed by mother who is at MMC.

Exclusion criteria:

- Intubated status
- Use of inhaled nitric oxide
- Persistent pulmonary hypertension of the newborn
- Presence of seizures on EEG
- Use of vasopressors or paralytic agents
- Presence of chest tubes, wound vacuum or drains
- Neonatal abstinence syndrome

Eligibility for enrollment and consent process: [name] is the Neonatal Neurologist involved in the clinical care of all infants at MMC treated with therapeutic hypothermia. [name] will describe the research study to parents of infants who meet the inclusion criteria. [name] and/or the co-investigators will obtain signed informed consent from the mother on behalf of herself and from the mother or father on behalf of the infant.

Intervention: After obtaining consent, on the second or third day of hypothermia treatment, consented mothers will be assisted with holding their infants for a single 30-minute period. Holding will take place with the assistance of the NICU nurse according to the protocol developed for this study (see attached). The infant's vital signs will be measured before, during and after holding. Esophageal temperatures will also be measured and recorded every 2 minutes during holding to ensure that holding does not impact the infant's body temperature. If temperature deviations $+\text{-}1^{\circ}\text{C}$ occur or if the infant becomes hypoxic with oxygen saturations below 90%, the holding session will be terminated and the baby will be returned to his or her isolette. Prior observation of therapeutic hypothermia indicates that 1 degree Celsius is the average temperature deviation that occurs in typical therapeutic hypothermia sessions.¹⁰

Implementation of questionnaires:

- Parent Questionnaire:
A questionnaire using the Likert scale will be administered on paper to mothers 30-60 minutes after completion of the holding session. Results will be linked by a patient identification number to the hormonal samples. Responses to the questionnaire will be entered into a password-protected REDCap database.
- Nurse Questionnaire:

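### The convenience sample of ten dyads leaves open which eligible families are approached and keeps no record of those passed over; consecutive approach with a log would reduce and expose that selection

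*Combined protocol and SAP*

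**What the plan says.** Section C, Study Population, gives the sampling method and its reason together. The reason is "As this is a pilot study to investigate concept and feasibility", and the method is that "a convenience sample of ten infants and their mothers in the MMC NICU being treated with TH will be recruited". No power or precision argument is offered for ten.

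The paragraph on eligibility and consent describes a clinician who "is the Neonatal Neurologist involved in the clinical care of all infants at MMC treated with therapeutic hypothermia". Its next sentence says that a named person (redacted; read here as the same clinician) "will describe the research study to parents of infants who meet the inclusion criteria". It does not say all parents, consecutive parents, or parents in any order.

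Other steps narrow the sample openly:

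- Clinical stability on limited or no respiratory support, of which the inclusion list says "This criterion MUST be confirmed by the Attending Neonatologist".
- "Informed consent for research study signed by mother who is at MMC".
- A single hold "on the second or third day of hypothermia treatment", with no rule for choosing the day.
- Staffing: Section B has an experienced NICU nurse move the infant "with assistance from a member of the research team".

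Under Data collected, Section C says that every infant cooled in this unit is already in a REDCap database. Section D compares adverse events with historical controls from the hypothermia database and states no matching or restriction. The document describes no screening log and no count of families not approached or declining. The holding procedure it refers to as an attachment is not in the file.

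**The concern.** Aim 1 concerns stable infants, so restriction to stable infants is the declared target and not a bias. The gap comes one step later, among infants who already meet every criterion. If the team can decide whom to approach, infants expected to tolerate the hold and mothers expected to welcome it may be approached first. The first tendency would favour the safety hypothesis; the second would favour the hypothesis of positive maternal responses. Both push the same way, and nothing in the planned data would show that it had happened.

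Two features add to the stakes. The safety comparison is with historical controls, so any further selection of the held infants adds to an existing lack of comparability. Aim 1 also claims feasibility, and without counts of eligible, approached, declined and missed dyads the report cannot say in what share of eligible dyads a hold was achieved.

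**Working it through.** **The plan's own figure.** The only figure is n = 10. It comes with no error rate, event rate, margin or consent rate, so there is nothing to reproduce. All risks below are assumptions, used only to show how much selection at the approach step could matter.

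**Set-up.** Suppose half the eligible infants have a lower event risk *a* during a hold and half a higher risk *b*, and that consent is unrelated to risk. Let *s* be the share of lower-risk infants among those held. The mean risk is *s·a* + (1 − *s*)·*b*. Consecutive sampling has *s* = 0.5; perfect sorting has *s* = 1. With independent holds, the chance of no events in ten is (1 − mean risk)^10.

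| Assumed risks *a* / *b* | *s* if selective | Selective: mean risk, P(0 of 10) | Consecutive: mean risk, P(0 of 10) |
|---|---|---|---|
| 5% / 25% | 0.60 | 13%, 0.87^10 = 0.25 | 15%, 0.85^10 = 0.20 |
| 5% / 25% | 0.75 | 10%, 0.90^10 = 0.35 | 15%, 0.85^10 = 0.20 |
| 5% / 15% | 1.00 | 5%, 0.95^10 = 0.60 | 10%, 0.90^10 = 0.35 |
| 5% / 25% | 1.00 | 5%, 0.95^10 = 0.60 | 15%, 0.85^10 = 0.20 |

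For the first row, the selective risk is 0.6 × 0.05 + 0.4 × 0.25 = 0.13. If *s* is 0.5 in practice, because every eligible family is approached, the two columns coincide and there is no bias from this source.

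**What consecutive approach leaves behind.** Consent is still voluntary. If a fraction *c* consents, and positive response rates would be *p* in consenters and *q* in decliners, the overstatement is *p* − [*c·p* + (1 − *c*)·*q*] = (1 − *c*)(*p* − *q*). Assume *p* = 95% and *q* between 60% and 80%:

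- *c* = 90%: 0.1 × (0.15 to 0.35) = 1.5 to 3.5 points
- *c* = 70%: 0.3 × (0.15 to 0.35) = 4.5 to 10.5 points
- *c* = 50%: 0.5 × (0.15 to 0.35) = 7.5 to 17.5 points

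**Families to approach.** On consent alone, 10/*c* rounded up gives 12, 15 or 20 families at 90%, 70% or 50% consent. The number of holds stays ten.

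**Precision, which the change does not affect.** With 0 of 10 events, the upper limit is 1 − 0.05^(1/10) = 25.9% (one-sided 95%) or 1 − 0.025^(1/10) = 30.8% (two-sided 95%).

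**The case against.** A reader might infer that staff will hand-pick calm infants and keen mothers. The document does not say so. Its consent paragraph can be read as approaching every family that meets the criteria, and a convenience sample may mean no more than whoever is eligible and available at one site. This objection stands: selective approach is permitted, not stated, and the results could be biased rather than are biased.

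A reader might also infer that consecutive approach would remove the bias. It would not. Consent, the mother's presence on site, the attending's judgement, the open choice of day and the unmatched historical controls all remain, and keenness in mothers acts at least partly through consent.

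The perfect-sorting rows need a threefold or fivefold risk gap to survive a long exclusion list, and a recruiter who can see it. The document does not show that a recruiter could foresee rewarming, line dislodgement or desaturation. With mild sorting the difference is 25% versus 20%. Aim 2 also surveys nurses, and choosing keen mothers has no evident route to nurses' answers.

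Finally, this is an openly labelled pilot of ten dyads, and imprecision will limit its safety conclusions whatever the sampling. That limits the weight of the point. It is no reason to leave the approach rule unstated, because a log costs little and a biased approach could not be detected without one.

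**Conclusion.** The point holds in a limited form. The sampling method is stated as convenience, and no rule in the document obliges the team to approach all eligible families or to record those it does not. Selection within the eligible group could therefore flatter the safety result and the mothers' responses, and would leave no trace.

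Its size cannot be estimated from the document. Under the assumptions shown, the chance of a clean 0 of 10 is raised by anything from nothing (all families approached), through 5 percentage points (mild sorting), to 40 points (perfect sorting with 5% and 25% risks). The upper end is an extreme case. No sample-size or error-rate figure changes. For a pilot of this size it is a modest point, worth acting on because it touches both aims.

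That the change would cost almost nothing is also more than the document supports. The infants are already known to the clinical team and already in a database, so logging is cheap. The effect on recruitment is unknown, because no accrual, eligibility or consent rate is given and each hold needs specific staff.

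**What to change.** In Section C, Study Population, replace the convenience-sample phrase with: *consecutive eligible infants, each family approached in order of eligibility, until ten holds have been started*. Add that an eligible infant may be passed over only for a reason recorded that day, such as the mother being unavailable or no trained nurse being on shift.

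In Section D, add that the report will give the numbers eligible, approached, declined and missed, with reasons, and count consented dyads in whom no hold was started among the missed. Use the existing REDCap database for the denominator of all cooled infants. Because eligibility includes the attending's confirmation, the log needs one line per eligible infant.

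State in the protocol that this reduces and exposes selection at the approach step, and list the sources that remain: consent, the mother-on-site condition, the stability judgement, the day of the hold and the historical comparison.

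The cost is a few sentences and a short log. The team gives up discretion over whom to approach, and recruitment may be somewhat slower. No eligibility criterion or clinical rule changes, and the target stays at ten.

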The Effects of Holding on Stress and Bonding in Mother-Infant Dyads During Therapeutic Hypothermia

Principal Investigator and Mentor: [name]
Co-Investigators: [name], MS4, [name], MS4

A. Introduction

Therapeutic hypothermia (TH) is a standard of care intervention that decreases death and disability in newborn term infants at risk for hypoxic brain injury. It involves placing the newborn infant on a cooling blanket for 72 hours in the Neonatal Intensive Care Unit (NICU). While TH has unmistakable neurological benefits to the newborn, prior research conducted with nurses and parents of infants treated with TH indicates that the experience is psychologically traumatic.¹⁻³ Specifically, both groups identified parents' inability to touch and hold their infants during TH as a major source of stress.

Past research demonstrates that the experience of being a patient in the NICU is associated with neonatal stress.⁴⁻⁶ Longitudinal studies show lasting effects of NICU-associated stress on infants as measured by persistent alterations in cortisol reactivity at eight months of age.⁷ It is likely that this stress profile also applies to infants who undergo TH while in the NICU. However, the association between TH and infant stress has not been studied quantitatively.

A complementary field of study has examined maternal holding as a therapeutic intervention for maternal and neonatal stress. Kangaroo, or skin-to-skin care, is widely used to facilitate mother-infant bonding and has been shown to have an analgesic effect on infants⁸ and cortisol lowering effects⁹ on mothers and infants. Likewise, oxytocin, a hormone produced by the pituitary gland and associated with maternal-infant bonding and stress reduction, has been shown to increase in mothers while they hold their infants¹⁴. It is unclear whether holding has the same effects during TH because skin-to-skin contact is not possible and morphine is often used to suppress infants' discomfort and shivering. The first specific aim of the present study is to evaluate the safety of allowing mothers to hold their infants during the TH protocol. The second specific aim is to investigate whether holding impacts mothers' and nurses' perception of stress during TH treatment.

[figure not shown]
B. Specific Aims and Significance

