The nurse questionnaire starts with an alteration of consent and consists of a combination of closed and open-ended questions that will be provided to the nurse on paper at completion of the holding procedure. The nurse's questionnaire will be identified by the case number that is assigned to the mother-infant dyad to protect their identities. The results of the questionnaire will be entered into a password-protected REDCap database.

Data collected:

As all of the patients treated with therapeutic hypothermia in our NICU are recorded in the Maine Medical Center Neonatal Encephalopathy REDCap database (IRB NET976245-1), we will use the same data for this holding study. In addition to the data already recorded in the REDCap database, we will also record the infant's current medication doses during holding, temperature recording taken at 2 minute intervals during holding and their vital signs before, during, and after holding. These vital sign recordings include temperature, heart rate, blood pressure, oxygen saturation and respiratory rate. If the infant does not have an arterial line in place, blood pressure will be measured every 10 minutes using a blood pressure cuff so as not to agitate the infant.

D. Analytical Methods

- Safety
Frequency of adverse events (as defined above) will be compared in this experimental cohort to data from historical controls in our therapeutic hypothermia database.
- Questionnaires
Answers from questions using a Likert scale will be simplified into nominal agree/disagree categories and compared with χ^2 test or Fisher's Exact Test as applicable. Open-ended responses will be analyzed by Thompson's general inductive technique.

E. References

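### Rewarming and desaturation are not ascertained alike in held infants and historical controls, so the Section D safety comparison can be biased in either direction

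*Combined protocol and SAP*

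**What the plan says.** Under Data collected, Section C says of the existing neonatal encephalopathy database that "we will use the same data for this holding study". It then adds: "In addition to the data already recorded in the REDCap database, we will also record" medication doses at the time of the hold, followed by "temperature recording taken at 2 minute intervals during holding and their vital signs before, during, and after holding". The vital signs listed include temperature and oxygen saturation. The Intervention paragraph gives the same sampling rule, "Esophageal temperatures will also be measured and recorded every 2 minutes during holding", for "consented mothers will be assisted with holding their infants for a single 30-minute period".

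The only safety analysis is in Section D: "Frequency of adverse events (as defined above) will be compared in this experimental cohort to data from historical controls in our therapeutic hypothermia database". The adverse effects set out in Section B are rewarming, with a 1°C threshold for stopping the hold, and dislodged central lines. Saturation below 90% appears only in Section C, as a reason to end the session.

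The plan does not give the database's fields or charting interval, the period over which a control is counted, or how a rewarming or desaturation event would be recognised in a control. It does not restrict the comparison to events that both sources capture.

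**The concern.** An event rate depends partly on how often, and for how long, one looks. Held infants are read every 2 minutes by staff watching for a threshold. Controls contribute whatever the database holds, over a period the plan leaves open. For an event that is found only by measuring, a difference between the groups can then come from the measuring.

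What is at stake is the Aim 1 hypothesis of no increase in adverse events during holding. An apparent excess could come from closer monitoring, a real excess could be dismissed as closer monitoring, and a long control window could hide a real excess. Better matching of controls on eligibility would not cure this, because the problem is how events are found and not which infants are chosen.

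**Working it through.** The plan states no event rate, power or test for the safety comparison, so there is no figure to reproduce. The steps below use the protocol's own numbers where they exist and mark assumptions where they do not.

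**1. Which events depend on the added readings**

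| Event | Held infants | Historical controls |
|---|---|---|
| Rewarming | 2-minute esophageal readings, plus before and after | Interval and window not stated |
| Saturation below 90% (a reason to end the session, not listed as an adverse effect) | Vital signs before, during, after | Interval and window not stated |
| Central line dislodgement | Seen when it happens | Does not depend on the added readings; database capture not stated |

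**2. Reading count.** 30 min / 2 min = 15 intervals, or 16 readings with a baseline.

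**3. Bias against holding.** Take an excursion lasting d = 10 min (assumption) and control charting every s min (assumption). The chance that it is charted is min(1, d/s).
- Held, s = 2: 1.
- Control, s = 15: 10/15 = 0.67. s = 30: 10/30 = 0.33. s = 60: 10/60 = 0.17.

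**4. Bias in favour of holding.** Section A describes cooling as follows: "It involves placing the newborn infant on a cooling blanket for 72 hours". If controls are counted over all of it, their observation time is 72 / 0.5 = 144 times that of a hold. Assume each reading has an independent 1% chance of being flagged:
- Held, 16 readings: 1 − 0.99^16 = 14.9%.
- Control, one reading in a matched half hour: 1.0%.
- Control, 72 hourly readings: 1 − 0.99^72 = 51.5%.

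The sign of the bias reverses on the choice of control window alone.

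**5. Effect on a test.** Assume Fisher's exact test, two-sided 0.05, with ten held infants (Section C) and equal true rates. Control numbers (16 or 50) and true rates are assumptions. Controls are detected either fully or at one-sixth, the 10/60 case in step 3. The chance of p ≤ 0.05, by full enumeration, is:

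| Controls | True rate | Equal detection | One-sixth detection |
|---|---|---|---|
| 16 | 10% | 0.014 | 0.054 |
| 16 | 30% | 0.027 | 0.336 |
| 50 | 10% | 0.016 | 0.151 |
| 50 | 30% | 0.031 | 0.505 |

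Unequal detection matters a good deal if events are common and much less if they are rare.

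**6. How common a 1°C event would be with no holding effect.** Simulate 16 readings around 33.5°C as a first-order autoregressive series, with correlation 0.8, 0.9 or 0.95 between successive readings (assumption). With SD 0.25°C (assumption, which makes the 33-34°C usual range about ±2 SD):
- Any reading more than 1°C from 33.5°C: 0.09%, 0.07%, 0.05%, against about 0.006% for a single reading.
- Rise of more than 1°C from the first reading: 0.75%, 0.17%, 0.01%.
- Change of more than 1°C from the first reading, either direction: 1.5%, 0.3%, 0.02%. Across ten infants that is at most 10 × 0.015 = 0.15 expected events.

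With SD 0.5°C (assumption), any reading more than 1°C from 33.5°C occurs in 17% to 34% of holds, against about 4.6% for a single reading. The answer therefore runs from negligible to large on an SD that the documents do not give.

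**The case against.** The strongest reply has four parts.

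- **Earlier infants did have temperatures recorded.** Section B reports a usual range from 16 earlier medical records, and Section C cites prior observation of temperature deviation. A reader might infer from the word for added data that controls were never measured for these events; that does not follow. This part stands. However, those 16 were a chart review, so they do not show that the database holds readings comparable with 2-minute sampling.
- **The thermal threshold is 1°C.** A reader might count readings outside 33-34°C, where the SD 0.25°C model gives 17% to about 33% with 16 readings against about 4.5% with one, and quote a 4- to 7-fold inflation. The protocol describes 33-34°C as a usual range, not as an adverse event. At 1°C the same model gives rates under 0.1% for a departure from 33.5°C and under 1% for a rise from the first reading. This part stands, and no such ratio should be quoted.
- **Not every event is affected.** Line dislodgement is not found by temperature or saturation readings, and saturation below 90% may not be in the comparison at all. This stands; it would be too broad to say that Aim 1 cannot be judged.
- **This is a ten-infant feasibility pilot** with no stated safety test, and the before, during and after vital signs give within-infant data on temperature without any controls. This limits the consequence, but the historical comparison is still the only safety analysis that Section D describes, and Section D does not mention a within-infant analysis.

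**Conclusion.** The point holds for events that are found by measuring: rewarming, and saturation below 90% if it is counted. The held infants' added readings cannot exist for controls, the database is not stated to contain comparable ones, and nothing in the plan equalises the ascertainment. Line dislodgement is outside the point.

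Neither direction nor size can be fixed from the documents. A reader might infer that the bias must run against holding. That holds only if controls are counted over a window about as short as the hold; over 72 hours it could run the other way. The figures in the working illustrate mechanism and range. They rest on assumed charting intervals, flag rates, event rates, control numbers, SD and correlation, and none is an estimate for this trial. The change is worth making before the comparison is run, because it is cheap and removes a bias that could not be separated from a holding effect afterwards.

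**What to change.** Amend Section D (Safety) as follows.

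1. List the events that enter the comparison, and say whether saturation below 90% is among them.
2. Limit the historical comparison to events ascertained the same way in both groups, such as line dislodgement if the database records it.
3. Compare temperature events with controls only over a window of equal length on the same day of cooling, with held infants' readings thinned to the controls' charting interval. State that interval. If it is so sparse that one reading or none per hold would remain, drop this comparison.
4. Report all other excursions and desaturations found only through hold monitoring descriptively, using each infant's own before, during and after readings, and do not set them against historical rates. The plan gives the 2-minute interval only for the hold itself, so compare levels across the three periods and not event counts, unless before and after readings are taken at the same interval.

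The cost is wording, a check of the database's fields and charting interval, and some data handling. No extra infants are needed. The downside is that fewer event types can be compared with historical rates.

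### Heart rate, blood pressure and respiratory rate are recorded around the hold but enter no safety result, so the Aim 1 conclusion does not cover them

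*Combined protocol and SAP*

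**What the plan says.** Section B states the Aim 1 safety hypothesis as "there will be no increase in adverse events during holding". Under Adverse Effects, the same section says that "potential adverse effects of the holding intervention and the monitoring strategy for these adverse effects are outlined here" and gives two numbered items. The first is "Holding during hypothermia could result in unintentional rewarming of the infant due to the proximity of the normothermic mother". The second is "Holding during hypothermia could result in dislodging of central lines".

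Section C (Intervention) adds criteria for ending a session: a temperature deviation of 1°C in either direction, or low saturation ("if the infant becomes hypoxic with oxygen saturations below 90%, the holding session will be terminated"). It also has vital signs taken before the hold, while it lasts and once it is over. Section C (Data collected) names them: "These vital sign recordings include temperature, heart rate, blood pressure, oxygen saturation and respiratory rate". For infants without an arterial line, "blood pressure will be measured every 10 minutes using a blood pressure cuff".

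Section D (Safety) contains one analysis: "Frequency of adverse events (as defined above) will be compared in this experimental cohort", set against historical controls from the unit's hypothermia database.

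**The concern.** The plan collects five vital signs around each hold, and its only safety analysis counts events defined earlier in the text. Three of the five, heart rate, blood pressure and respiratory rate, appear in none of those definitions. The plan clearly regards cardiorespiratory stability as important: it excludes infants on vasopressors or inhaled nitric oxide and those with pulmonary hypertension, and an attending must confirm stability. Yet a stable infant whose heart rate or blood pressure changes on being moved and held would leave no trace in the planned result.

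What is at stake is the reach of the conclusion. A report of no increase in adverse events would naturally be read as saying that infants tolerated holding. As planned, it would cover temperature, lines and perhaps saturation, and nothing else. If what counts as an event for the other three signs is decided only once the readings have been seen, the choice is post hoc. With ten infants, one infant classified differently moves the reported rate by 1/10, or 10 percentage points.

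**Working it through.** The plan states no event rate, margin, power or alpha, and ten is a convenience sample, so there is no figure of its own to reproduce. The check is mainly textual.

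**Step 1. Trace each recorded sign through the plan.**

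| Recorded sign (Section C) | Adverse Effects list (Section B) | Criterion for ending the hold (Section C) | Route into the Section D count |
|---|---|---|---|
| Temperature | Item 1, rewarming | Yes | Yes |
| Oxygen saturation | None | Yes, below 90% | Only if ending criteria count as defined events |
| Heart rate | None | None | None |
| Blood pressure | None | None | None |
| Respiratory rate | None | None | None |

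Line dislodgement, item 2, is an event but not a vital sign. Even on the widest reading of the definitions, three of the five recorded signs have no route into the safety result, and Section D plans no separate summary of them.

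**Step 2. How often could this matter?** The documents give no rate of heart rate, blood pressure or respiratory changes per hold, so the rates below are assumptions. With n = 10 holds, treated as independent, P(at least one) = 1 − (1 − p)^10.

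| Assumed p per hold | Calculation | P(at least one in ten) | Expected number (10p) |
|---|---|---|---|
| 1% | 1 − 0.99^10 | 9.6% | 0.1 |
| 2% | 1 − 0.98^10 | 18.3% | 0.2 |
| 5% | 1 − 0.95^10 | 40.1% | 0.5 |
| 10% | 1 − 0.90^10 | 65.1% | 1 |
| 20% | 1 − 0.80^10 | 89.3% | 2 |
| 30% | 1 − 0.70^10 | 97.2% | 3 |

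The lower rows deserve as much weight as the upper ones, because enrolled infants must be clinically stable, not intubated and off vasopressors.

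**Step 3. What would a clean result cover?** With 0 events in 10, the exact two-sided 95% upper limit is 1 − 0.025^(1/10) = 30.8% (one-sided, 1 − 0.05^(1/10) = 25.9%). That limit applies only to the event types counted. It says nothing about the three uncounted signs.

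**Step 4. What could the existing readings show?** With ten infants, the 95% CI for a mean paired change has half-width t(0.975, 9 df) × s/√10 = 2.262 × s/3.162 = 0.72 s, where s is the SD of the within-infant changes. This is imprecise but informative, and it needs no historical data.

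**The case against.** **The holding protocol is unseen.** Section C refers to an attached holding protocol that is not in the supplied text and may contain further criteria. This stands, and the point is limited accordingly. Even if criteria exist there, Section D refers to definitions above it and would need to point to the attachment.

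**No sentence declares such holds event-free.** A reader might infer that any hold with bradycardia, apnoea or a blood pressure fall is scored as free of adverse events. The documents do not support that without qualification. It is an inference from the reference to earlier definitions, and apnoea that takes saturation below 90% would end the session and might then be counted. The claim holds only for changes without such desaturation.

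**Bias is not shown.** A reader might also infer that the result is tilted in favour of holding. If the same event definition is applied to the historical controls, leaving out an event type does not by itself favour either group. The supported criticism is that the safety assessment is incomplete in scope.

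**Adding events to the count could do harm.** Section C says the readings around the hold are recorded in addition to what the database already contains, so controls may have nothing equivalent. Counting new event types in held infants only would bias the comparison against holding. This stands and shapes the fix.

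**Blood pressure sampling.** A reader might infer that the plan already has a distortion between arterial-line and cuff infants. The plan gives no arterial reading interval and has no blood pressure endpoint, so this is something for a new analysis to guard against, not a present error.

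**Conclusion.** The point holds in limited form. In the protocol text as supplied, heart rate, blood pressure and respiratory rate are recorded but appear in no adverse-effect item, no criterion for ending a hold and no planned analysis. A change in them without saturation below 90% does not enter the Aim 1 result, so a finding of no increase in adverse events would not extend to cardiorespiratory tolerance.

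This rests on the text alone and needs no assumed rate. Its practical size is unknown: the chance that at least one of ten holds is affected runs from 9.6% to 97.2% as the assumed rate per hold runs from 1% to 30%. The plan should be changed, because the data are to be collected anyway and only the pre-specified definition and summary are missing.

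**What to change.** In Section D (Safety), add a within-infant analysis of the heart rate, blood pressure and respiratory rate readings:

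- For each sign, report the paired change from before to during the hold, and from before to after it, with 95% CIs.
- Report the number of the ten infants with a new out-of-range value during or after the hold, with an exact 95% CI. The investigators set the ranges before the first hold.
- Use the same number of readings in each period, so that a period with more readings does not show more abnormal values by opportunity alone. For blood pressure, use the same 10-minute time points in all infants and one method per infant.
- State whether sessions ended for temperature or saturation count as adverse events.
- Present these results beside the temperature, saturation and line events. Keep them out of the historical-control comparison unless the database holds equivalent readings.

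No change to when a hold is ended is proposed.

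The cost is a few lines in Section D, the ranges on the data form and slightly more analysis. The plan gives no reading frequency for heart rate or respiratory rate and no number of readings before or after the hold, so the form should fix these; where periods differ, the analysis can be restricted to a matched subset of readings. The one downside for the investigators is that the reported event count can only stay the same or rise.
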